### **3.5.4 Prior and Subsequent Systemic Therapies**

Systemic therapy regimens are collected on two CRFs:

- Prior Systemic Therapy
- Subsequent Systemic Therapy

Medications collected on both CRFs will be coded by Pfizer to preferred terms by means of the World Health Organization Drug Dictionary (WHODRUG).

Subjects reporting multiple medications within the same PT will be counted only once for that PT on medication summaries. PTs in summaries will be displayed in order of decreasing total frequency of occurrence.

Prior Systemic Therapies will be summarized by PT and by:

- Initial assigned dose levels or initial assigned dosing schedules (in the case of Part 4 biweekly) for Part 1 and Part 4 (Dose Escalation cohorts)

- Monotherapy or combination therapy for Part 2 and Part 3
- Indication within monotherapy and by combination therapy for Part 2 and Part 3

In addition, a listing will be provided that contains the verbatim medication term, PT, therapy start and end dates, study drug start date, duration of therapy, route of administration, best overall response, and the reason the therapy ended.

Subsequent Systemic Therapies will be summarized by PT. In addition, a listing will be provided. This listing will contain the verbatim medication term, PT, therapy start date, and the study day on which the therapy started.

### **3.5.5 Blood Transfusions**

Blood transfusions performed during the study will be summarized by the number and percent of subjects having each transfusion element (platelets, packed red blood cells, etc.). For each subject and transfusion element, the total number of transfusions and cumulative element units will be calculated. These calculated values will be summarized by descriptive statistics.

A listing will be provided containing each subject's blood transfusion data and transfusion-related medical history.

### **3.5.6 Antidrug Antibodies**

The analysis of antidrug antibodies will be performed by Sarah Cannon Development Innovations.

Final individual subject results from the ADA and NAb assay (as appropriate) will be presented in the listings and the incidence summarized by descriptive statistics in tabular form by cohort.

Summary tables that show the number and percentage of subjects that fall into the following categories will also be produced by cohort:

Treatment-induced ADA	Baseline ADA titer is missing or negative and subject has $\geq 1$ post-treatment positive ADA titer.
Treatment-boosted ADA	Baseline ADA titer is positive and subject has a $\geq 4$ -fold dilution increase in ADA titer from baseline in $\geq 1$ post-treatment sample. If ADA titer is log10 transformed, a 4-fold dilution increase is equivalent to 0.602 unit increase in titer (log10) from baseline. If ADA titer is log2 transformed, a 4-fold dilution increase is equivalent to 2 unit increase in titer (log2) from baseline.
ADA-positive subject	A subject with $\geq 1$ treatment-induced or treatment-boosted ADA response.
ADA-negative subject	An ADA evaluable subject without treatment-induced or treatment-boosted ADA response. Subject either has (1) all ADA-negative results

	throughout the study or (2) is ADA positive at baseline but did not become treatment-boosted post-dose.
ADA incidence	The percent of ADA- positive subjects in a treatment group/cohort or study.
Treatment-induced NAb	Baseline NAb titer is missing or negative or ADA-negative and subject has $\geq 1$ post-treatment positive NAb titer.
Treatment-boosted NAb	Baseline NAb titer is positive and subject has a $\geq 4$ -fold dilution increase in NAb titer from baseline in $\geq 1$ post-treatment sample. If NAb titer is log10 transformed, a 4-fold dilution increase is equivalent to 0.602 unit increase in titer (log10) from baseline. If NAb titer is log2 transformed, a 4-fold dilution increase is equivalent to 2 unit increase in titer (log2) from baseline.
NAb-positive subject	An ADA-positive subject with $\geq 1$ treatment-induced or treatment-boosted NAb response. For ADA-positive (treatment-boosted) subjects, subject is NAb positive only if the subject has $\geq 1$ treatment-induced or treatment-boosted NAb response at the visit where the subject has a treatment-boosted ADA response. For visits where the subject did not show a boosted ADA response, the subject is classified as NAb-negative for the visit even if the subject has post-treatment positive NAb titer for that visit.
NAb-negative subject	NAb evaluable participant who is either (1) an ADA-negative subject or (2) an ADA-positive subject without treatment-induced or treatment-boosted NAb response (i.e. subject has all NAb-negative results throughout the study or subject is NAb positive at baseline but did not become treatment-boosted post-dose). Note: in the event a subject is ADA-positive at baseline but did not show a boosted response post-treatment, subject is classified as ADA-negative and NAb-negative at the subject level even if the subject has post-treatment positive NAb titer. As such all ADA-negative subjects are NAb-negative regardless of NAb titer data."
NAb incidence	The percent of NAb- positive subjects in a treatment group/cohort or study.
Transient ADA	An ADA-positive subject with (1) a treatment-induced or treatment-boosted ADA sample detected only at 1 sampling time (excluding the last time point) post-treatment, or (2) treatment-induced or treatment-boosted ADA samples detected at $\geq 2$ time points where the first and last positive samples (irrespective of any negative samples in between) are separated by $< 16$ weeks, and the subject's last sample is ADA negative.
Persistent ADA	An ADA-positive subject with first and last positive ADA samples (treatment-induced or treatment-boosted) detected over a period of $\geq 16$ weeks post-treatment, irrespective of any negative samples in between

Indeterminate ADA	An ADA-positive subject who is not persistent or transient
Transient NAb	A NAb-positive subject with (1) a treatment-induced or treatment-boosted NAb sample detected only at 1 sampling time (excluding the last time point) post-treatment, or (2) treatment-induced or treatment-boosted NAb samples detected at $\geq 2$ time points where the first and last positive samples (irrespective of any negative samples in between) are separated by $< 16$ weeks, and the subject's last sample is NAb negative or ADA negative
Persistent NAb	A NAb-positive subject with first and last positive NAb samples (treatment-induced or treatment-boosted) detected over a period of $\geq 16$ weeks post-treatment, irrespective of any negative samples in between.
Indeterminate NAb	A NAb-positive subject who is not persistent or transient.

Titers will be reported if applicable.

## 3.6 Pharmacokinetic Analysis

The PK analysis will be performed by Pfizer and reported separately. Sarah Cannon Development Innovations will provide the PK listing to be included in the CSR.

### 3.6.1 Serum Concentrations

Pharmacokinetic blood samples for determination of TTI-621 serum concentrations will be collected in accordance with the regimen specified in the schedule of events. The concentrations as reported by the bioanalytical lab will be used without rounding for all analyses.

For serum concentration data, all values below the limit of quantification (BLQ) will be set to 0 for summary statistics and graphs. Individual serum concentrations of TTI-621 will be summarized at each time point using descriptive statistics. Individual concentration plots and median data by dose cohorts graphs will be produced. All graphs will be presented using both linear and semi-logarithmic scales. The above descriptive summary will be performed for the PK-evaluable Set.

All TTI-621 serum concentrations will be presented in a by-subject listing. Additionally, time elapsed since dosing and deviation from scheduled time point will be presented.

### 3.6.2 Pharmacokinetic Parameters

Pharmacokinetic parameter estimation will be performed using non-compartmental analysis on individual serum concentration-time data. The actual sampling times will

be used for all calculations, except as noted above. For the PK parameter calculation, BLQ serum concentrations occurring before Tmax will be set to 0, except for a BLQ value occurring between two measurable concentrations, in which case it will be set to missing. BLQ concentrations occurring in pre-dose (trough) samples during the multiple dosing phase will be set to zero. Pharmacokinetic parameter estimates and summaries will be completed for subjects in the PK Population having sufficient measurable concentrations to define the PK profile. For any subject whose extrapolated AUC from the last time point where the concentration is above the limit of quantification to infinity exceeds 20% of the total AUC, the  $AUC_{0-\infty}$  from the subject will be excluded from the calculation of the descriptive statistics.

Pharmacokinetic parameter estimates after the single dose will include Cmax, Tmax,  $AUC_{0-t}$ ,  $AUC_{0-168}$  where appropriate and as data permit. For the multiple dosing phase, Cmax, Tmax, Cmin, Cavg,  $AUC_{0-t}$ ,  $AUC_{0-\tau}$ , CL will be calculated if data permit. Additional PK parameters may be reported if appropriate.

The non-compartmental parameters will not be reported to any greater precision than that of the concentration data. All parameters will be reported to 3 significant figures. Parameter values will be rounded to the same precision used in data listings prior to any statistical analysis or descriptive summaries.

The below precision will be used for descriptive and statistical summary of PK parameters:

1. Geometric Means, Medians and their %CV and Confidence Intervals (CIs) – 1 more significant figure than the data
2. Standard Deviation – 1 more significant figure than means
3. CV% – whole numbers
4. Minimum, Maximum – same significant figures as the data
5. Ratios, CIs (log transformed data) – 2 decimal places

For parameters which are direct time observations, Median and Range will have the same significant figures as the data.

The definitions and the associated rules for the PK parameter calculation are summarized in the table below.

Cmax	Maximum observed concentration, occurring at time Tmax. If all observations are below the limit of quantification (BLQ), Cmax will be reported as zero.
Tmax	Time of maximum observed concentration. If the maximum observed concentration is not unique, then the first maximum is used. If all observations are BLQ, Tmax will be reported as not determined (ND).
$AUC_{0-t}$	Area under the curve from the time of dosing to the time of the last measurable concentration calculated using the trapezoidal rule. If all concentrations are BLQ, $AUC_{last}$ will be reported as zero
Cmin	Minimum observed concentration occurring at time Tmin.
$AUC_{0-\tau}$	The partial area from dosing time to Tau, (i.e. 0-168 h).

Rac (Multiple dosing)	Observed accumulation ratio will be calculated as: Rac = AUC T,ss / AUC T,(first dose) .
CL	An estimate of total body clearance computed from the steady state data, calculated as Dose/AUC 0-tau .
Cavg	Average concentration during a dosing interval, calculated as AUC 0-tau divided by tau.

The calculated PK parameters will be summarized using descriptive statistics, including arithmetic and geometric means, SD, arithmetic and geometric %CV, median, minimum, and maximum. For Tmax only the median and the range will be reported. All data will be summarized by subject, dose, cohort and the study part.

Dose proportionality will also be assessed based on the data acquired during the dose escalation phase using descriptive statistics.

TTI-621 serum concentrations from this study may be pooled with data from other studies and analyzed using population PK approaches. In addition, a model-based approach may be used to explore the potential relationship between TTI-621 exposure metrics and efficacy, safety, and/or biomarker endpoints. These analyses, if conducted, will be reported in separate report(s).

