### 3.3.2 Phase 1b Dose Optimization Part 4 (to be enrolled as of Amendment 9)

A minimum of 3 patients will be treated in each cohort sequentially in a 3 + 3 design. The planned dose escalation levels are shown in [Table 3-4](#). Patients will receive once weekly dosing of TTI-621 at the dose levels in their assigned cohort regimen (Week 1 given on Day 1, Week 2 given on Day 8, and Week 3 given on Day 15). The DLT observation period is 21 days. Patients will be considered evaluable for DLT if they receive all 3 weekly doses within the DLT evaluation period or if they experience an AE meeting DLT criteria during that time. If a patient experiences a non-DLT event that requires a dose to be held per dose modification guideline ([Section 6.5](#)), the DLT evaluation period can be extended to 28 days. If a DLT occurs in 1 of 3 patients within a cohort, 3 additional patients will be treated at that cohort regimen. In the absence of DLT, enrollment will proceed sequentially through the planned dose levels.

Alternative dose escalation including evaluation of intermediate doses, expansion of an existing dose level, evaluation of alternative regimens/schedules including a dose ramp-up design following different dose intensification increments and schedule, and modification of dosing frequency and/or IV infusion rate are all permissible if supported by the evolving data and a SRC decision. All patients in each cohort must have completed the 21-day DLT period before the next cohort begins treatment. The MTD of TTI-621 will be the dose below the one in which  $\geq 2$  DLTs are observed among 6 treated patients.

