### **1.2.5 Phase 1b Dose Optimization – Part 4**

In the dose optimization phase, Part 4, the safety and tolerability of TTI-621 at higher dose levels beyond the initially recommended Phase 1b dose of 0.2 mg/kg (as determined during Phase 1a dose escalation) and the highest dose of TTI-621 evaluated (0.5 mg/kg) during Phase 1b dose expansion following dose intensification permissible per protocol, will be evaluated. This Phase 1b dose optimization phase will aim at re-defining MTD following 3+3 dose escalation schema and a revised DLT criteria based on the totality of safety data collected thus far from Phase 1a and 1b dose expansion phase of the study. In Phase 1b dose optimization of the study (Part 4), further dose escalation of TTI-621 will be pursued in subjects with relapsed and/or refractory CTCL following a 3+3 escalation design and using a revised DLT criteria. Dose optimization will proceed following review of the data obtained from the Phase 1b Part 3, stage 1 cohorts of CTCL and PTCL subjects. Alternative dosing schedules, intermediate doses, and other optimization options may be considered by the SRC following review of available data.

Part 4 Q2W is an expansion to Part 4 Cohort 5 (P4-5). Dosing is done at the 2.0 mg/kg dose level and explores a TTI-621 biweekly (every other week) dosing schedule.

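### SAP 3.6.2 sets tau at 168 h without exception, so CL and Cavg for the Part 4 Q2W cohort, applied as written, cover only half the 336 h dosing interval

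*SAP*

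**What the plan says.** The parameter table in SAP 3.6.2 describes AUC0-tau as "The partial area from dosing time to Tau, (i.e. 0-168 h", and the bracket closes there. No cohort or schedule is excepted. Two other rows depend on it. CL is "An estimate of total body clearance computed from the steady state data, calculated as" Dose/AUC0-tau. Cavg is "Average concentration during a dosing interval, calculated as" AUC0-tau divided by tau. Rac is also a ratio of areas over tau, steady state to first dose. The text above the table plans these parameters subject to the data allowing them: "For the multiple dosing phase, Cmax, Tmax, Cmin, Cavg", followed by AUC0-t, AUC0-tau and CL. After a single dose it lists AUC0-168 under its own name.

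Most Part 4 cohorts are weekly. Protocol 3.3.2 says: "Patients will receive once weekly dosing of TTI-621 at the dose levels in their assigned cohort regimen". SAP 1.2.5 adds a Part 4 Q2W cohort, of which it says: "Dosing is done at the 2.0 mg/kg dose level and explores a TTI-621 biweekly (every other week) dosing schedule".

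Elsewhere the SAP allows for this schedule. In SAP 3.4 the duration of TTI-621 treatment adds 14 days for Part 4 Q2W subjects and 7 days for everyone else. In SAP 2 the DLT-evaluable set leaves Q2W out. The PK section makes no such adjustment.

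**The concern.** Dose divided by AUC estimates clearance at steady state only when the AUC spans one full dosing interval. The average concentration over an interval likewise needs the whole interval in both the area and the divisor. For weekly subjects 168 h meets both conditions. For Q2W subjects it stops halfway: the area omits the second week, and the divisor is half the true interval.

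PK profile is a secondary endpoint for Part 4 (Protocol 8.1.3, SAP 1.1.3), and SAP 3.6.2 summarises parameters by dose, cohort and study part. Q2W values would therefore be reported beside weekly ones under the same labels while measuring something different. A clearance difference produced by the cut-off could be taken for a property of the drug. A Cavg averaged over only the first week after a dose would hide part of the fall in average exposure that a longer interval brings. SAP 3.6.2 also says that exposure metrics may enter later exposure-response modelling.

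**Working it through.** **Inputs.** tau as written, 168 h (SAP 3.6.2). Q2W interval, 14 × 24 = 336 h (SAP 1.2.5). Weekly interval, 7 × 24 = 168 h (Protocol 3.3.2). Half-life: no human value is given. The monkey range of 35.2 to 156 h (Protocol 1.6.4) is used only as an assumption to size the effect.

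**The plan's own figure.** 7 × 24 = 168 h reproduces the stated tau for weekly dosing. In a one-compartment steady-state model with a 1-hour infusion, Dose/AUC0-168 under weekly dosing returns the true clearance (ratio 1.000). The weekly cohorts are unaffected.

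**Q2W without a PK model.** At steady state Dose = CL × AUC0-336, so:

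- CL as written / true CL = (Dose/AUC0-168) / (Dose/AUC0-336) = AUC0-336 / AUC0-168.
- Cavg as written / true Cavg = (AUC0-168/168) / (AUC0-336/336) = 2 × AUC0-168 / AUC0-336.
- Product of the two = 2 exactly.

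The larger factor is therefore at least √2 = 1.414, so at least one parameter is overstated by 41% or more. The CL factor exceeds 1 whenever drug is measurable in week 2. The Cavg factor exceeds 1 whenever mean concentration is lower in week 2 than in week 1. When both conditions hold, both parameters are overstated.

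**Size under one-compartment kinetics.** AUC0-168/AUC0-336 = 1/(1 + 2^(−168/t½)), which gives a CL factor of 1 + 2^(−168/t½) and a Cavg factor of 2/(1 + 2^(−168/t½)).

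| Assumed t½ (h) | 2^(−168/t½) | CL factor | Cavg factor |
|---|---|---|---|
| 35.2 | 0.037 | 1.037 | 1.929 |
| 72 | 0.198 | 1.198 | 1.669 |
| 96 | 0.297 | 1.297 | 1.542 |
| 156 | 0.474 | 1.474 | 1.357 |

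A numerical check with a 1-hour infusion, superposition and trapezoidal areas agrees closely: at 35.2 h, 1.037 for CL and 1.929 for Cavg; at 156 h, 1.476 and 1.355. With tau = 336 h, the Q2W CL ratio returns to 1.000.

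**A mixed reading.** If the area stopped at 168 h but the divisor were 336 h, the Cavg factor would be AUC0-168/AUC0-336, from 0.96 (t½ 35.2 h) to 0.68 (t½ 156 h). That is an understatement.

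**The case against.** The strongest reply is that the 168 h is a leftover from weekly dosing that no PK analyst would apply to Q2W. The Cavg row itself refers to a dosing interval, which for this cohort is 336 h. The sponsor performs the PK analysis and reports it separately (SAP 3.6), the PK text was supplied for inclusion as it stood (SAP 1), and Protocol 8.4.5 allows a final PK analysis plan that may define tau by schedule. All of this bears on whether an error will reach a report. It does not change the fact that the only definition of tau in these documents is wrong for one cohort. A reader might infer that reported Q2W results are in error; the documents do not show that.

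Second, feasibility. Multiple-dose parameters are computed only if the data permit, and neither document gives Q2W PK sampling times. Whether a 168 h or a 336 h sample exists is unknown. This stands, and the fix has to allow for it. It limits what can be computed, not how it should be defined.

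Third, size. Protocol 1.6.4 calls the monkey half-lives extremely variable and reports exposure rising more than in proportion to dose, so a linear one-compartment model with those values is an illustration and sets no bounds for humans. This also stands. In particular, a reader might infer a large clearance error; with a short half-life it is about 4%, and nearly all of the distortion falls on Cavg.

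Fourth, purpose. A reader might infer that the cohort was set up as a formal comparison with weekly dosing, which this error would spoil. SAP 1.2.5 says only that it "explores a TTI-621 biweekly (every other week) dosing schedule". No test or decision rule uses CL or Cavg, and the PK summaries are descriptive.

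Nor does the point show that Rac is biased. Its two areas need only share an interval.

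**Conclusion.** The definition is wrong as written for the Part 4 Q2W cohort and correct for the weekly cohorts. If tau = 168 h is used literally in both the area and the divisor, the CL and Cavg factors multiply to 2 whatever the kinetics, provided steady state holds. At least one parameter is then overstated by 41% or more. Both are overstated if drug is still measurable in week 2 at a lower mean level than in week 1. The ranges of 1.04 to 1.47 times for CL and 1.93 to 1.36 times for Cavg rest on one-compartment kinetics and monkey half-lives. They run in opposite directions: the half-life that makes one error small makes the other large.

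The consequence is limited to descriptive secondary results: Q2W values that cannot be set beside the weekly ones. It is worth correcting because the conflict lies within the SAP itself and the correction is small.

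**What to change.** In the SAP 3.6.2 parameter table, define tau as the assigned dosing interval, 168 h for weekly cohorts and 336 h for Part 4 Q2W, and use it for AUC0-tau, CL and Cavg. For Rac, state that numerator and denominator use the same interval, and add first-dose AUC0-336 for Q2W to the single-dose parameter list, which now has only AUC0-168. Keep AUC0-168 as a separately labelled parameter for display across schedules. State that where a Q2W subject's sampling does not support AUC0-336, CL and Cavg are not reported for that subject, rather than computed over 168 h.

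The cost is a few small edits to SAP 3.6.2, in the single-dose list and the parameter table, with no new data collection. The price is that some Q2W subjects may have no reportable CL or Cavg. How many cannot be judged without the Q2W sampling schedule.

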#### 1.6.4 Nonclinical Pharmacokinetics

Pharmacokinetic (PK) investigations were conducted in conjunction with both the Good Laboratory Practice (GLP) and non-GLP primate toxicology studies. Across all studies, TTI-621 doses ranged from 0.5 to 12.5 mg/kg. Dosing was intravenous (IV) with the exception of 1 cohort of male monkeys given TTI-621 subcutaneously (SC) in Study 5001009. In general, both maximum blood concentration (Cmax) and area

under the curve ( $AUC_{0-\infty}$ ) increased in a more-than-dose-proportional manner. Mean terminal half-life ( $t_{1/2}$ ) values between all cohorts after the Day 1 dose were extremely variable, ranged from 35.2 to 156 hours, or approximately 1.5 to 6.5 days. The variation in  $t_{1/2}$  between cohorts did not appear to be a function of dose. SC dosing led to lower  $C_{max}$  and  $AUC_{0-\infty}$  and longer time to  $C_{max}$  ( $T_{max}$ ) values compared with IV dosing; however,  $t_{1/2}$  and other parameters were similar between SC and IV administration.

Trends in the PK parameters of later time points were inconsistent and variable relative to Day 1, which was likely a consequence of the development of antidrug antibodies (ADA) in the majority of animals.

Additional information may be found in the Investigator's Brochure.

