#### 7.14.2 PK

In both the escalation and expansion phases (Part 2), serial blood sampling will take place in conjunction with the first and sixth weekly infusion of TTI-621 (i.e., Days 1 and 36 of study) to estimate the PK profile of TTI-621. Subsequent sampling after the first week will be limited to "trough" levels (30 minutes pre-dose). A sample will also be taken at EOT.

For phase 1b Part 3 only, serial blood sampling will take place in conjunction with the first and eighth weekly infusion of TTI-621, a time at which mandatory intra-subject dose intensification for newly enrolled subjects is anticipated to be completed. This sampling will be performed to evaluate the PK profile of TTI-621 following dose-intensification, and after repeat dosing. Subsequent sampling will be limited to "trough" levels at Week 9 through Week 16 inclusive. A sample will also be taken at EOT.

For phase 1b Part 4, for subjects enrolled in cohorts without priming doses, serial blood sampling will take place in conjunction with the first and sixth weekly infusion of TTI-621 (i.e., Days 1 and 36 of study) to estimate the PK profile of TTI-621 with further dosing optimization. For subjects enrolled in cohorts with priming dose regimen under phase 1b Part 4 receiving a single priming dose on Week 1, serial blood sampling will take place on Week 2, following administration of the highest stable dose and on the sixth weekly infusion of TTI-621 to estimate the PK profile of TTI-621 with further dosing optimization. Subsequent sampling for all phase 1b Part 4 cohorts, will be limited to "trough" levels at Week 9 through Week 16 inclusive. A sample will also be taken at EOT.

If there is a delay in infusion administration (i.e., duration of TTI-621 infusion is greater than 60 minutes), the end-of-infusion PK sample should be drawn at the time the infusion is complete (prior to flush). However, all subsequent timepoints should

not be adjusted and should be collected relative to the start of TTI-621 infusion as summarized in [Table 7-2](#).

Whole blood will be collected at each time point and prepared as outlined in the separate Laboratory Manual.

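### The SAP's accumulation ratio has no dose term, so in Part 3 and in intensified combination subjects it mixes the planned dose increase with accumulation

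*SAP*

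**What the plan says.** The parameter table in SAP 3.6.2 states: "Observed accumulation ratio will be calculated as" AUC over tau at steady state divided by AUC over tau after the first dose. Tau is 168 h. Neither a dose term nor an unchanged-dose condition appears. Clearance, in the next row, is "An estimate of total body clearance computed from the steady state data" and does carry the dose (Dose/AUC). On presentation the SAP says: "All data will be summarized by subject, dose, cohort and the study part".

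The protocol fixes which profiles feed the ratio:

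- **Part 3.** Under Protocol 7.14.2, "serial blood sampling will take place in conjunction with the first and eighth weekly infusion of TTI-621". The eighth infusion is used because mandatory intensification should be finished by then. Protocol 6.4.1 and 6.5.4 start subjects at 0.2 mg/kg and raise the dose by 0.1 mg/kg per week from Week 3, as tolerated, to at most 0.5 mg/kg.
- **Combination cohorts.** Protocol 6.4.2 and 6.4.3 start TTI-621 at 0.1 mg/kg and require intensification of newly enrolled subjects under 6.5.4. Protocol 7.14.2 places the second Part 2 serial profile at the sixth infusion. Appendix D Table 1, which covers Parts 2 and 3, shows it at Week 8.
- **Priming cohorts (Part 4, if used).** Week 1 is 0.2 mg/kg, but "serial blood sampling will take place on Week 2, following administration of the highest stable dose", and again at the sixth infusion. Appendix F gives Week 1 only a pre-dose and an end-of-infusion PK sample.

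**The concern.** An accumulation ratio is meant to show how far exposure builds up when the same dose is repeated. If the numerator and denominator come from different doses, the ratio also contains the dose change. In Part 3 this happens by design for every subject who ramps up. A reader of the PK report could take a value well above 1 as drug build-up when part of it, possibly most of it, is the planned increase. What is at stake is the description of repeat-dose PK, which is a secondary objective.

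**Working it through.** The documents state no numerical Rac, so there is no figure to reproduce.

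**Inputs.** Doses and profile weeks are as above; tau = 168 h. Half-life is an assumption: Protocol 1.6.4 gives only monkey values, 35.2 to 156 h, and these limits are used as the range.

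**Ramp check.** Part 3 doses of 0.2, 0.2, 0.3, 0.4, 0.5 mg/kg reach 0.5 at Week 5, which agrees with the 5 to 8 weeks in Protocol 6.4.1. A combination ramp of 0.1, 0.1, 0.2, 0.3, 0.4, 0.5 reaches 0.5 at Week 6.

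**Formula.** For linear one-compartment IV kinetics, let r = exp(−ln 2 × 168 / half-life). AUC over the interval in week w is proportional to the sum over weeks j ≤ w of dose_j × r^(w−j). Hence Rac = [sum of dose_j × r^(w−j)] / dose_1. At constant dose it tends to 1/(1−r).

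- Half-life 35.2 h: r = 0.0366, constant-dose Rac = 1/(1−0.0366) = 1.04.
- Half-life 156 h: r = 0.474, constant-dose Rac = 1/(1−0.474) = 1.90.

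**Example.** Part 3 full ramp, Week 8 over Week 1, half-life 156 h: [0.5(1 + r + r² + r³) + 0.4r⁴ + 0.3r⁵ + 0.2r⁶ + 0.2r⁷] / 0.2 = 0.933/0.2 = 4.67. Divided by the dose ratio 0.5/0.2 = 2.5, this is 1.87.

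The dose share below is ln(dose ratio)/ln(Rac). Each pair is for half-lives of 35.2 h and 156 h.

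| Subjects and profiles | Dose ratio | Rac as written | Dose-normalised | Dose share of log Rac |
|---|---|---|---|---|
| Constant dose, Week 6/1 | 1.0 | 1.04; 1.88 | 1.04; 1.88 | 0 |
| Part 3, 0.5 from Week 5, Week 8/1 | 2.5 | 2.59; 4.67 | 1.04; 1.87 | 96%; 59% |
| Part 3, 0.5 only at Week 8, Week 8/1 | 2.5 | 2.58; 3.98 | 1.03; 1.59 | 97%; 66% |
| Part 3, stops at 0.3, Week 8/1 | 1.5 | 1.56; 2.84 | 1.04; 1.89 | 92%; 39% |
| Combination 0.1 to 0.5, Week 6/1 | 5.0 | 5.15; 7.86 | 1.03; 1.57 | 98%; 78% |
| Combination 0.1 to 0.5, Week 8/1 | 5.0 | 5.19; 9.14 | 1.04; 1.83 | 98%; 73% |
| Priming, Week 6/2 | 1.0 | 1.02–1.03; 1.57–1.74 | same | 0 |

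For accumulation alone to match a 2.5-fold dose change, 1/(1−r) = 2.5 gives r = 0.6 and a half-life of about 228 h (9.5 days). For 5-fold, r = 0.8 and about 522 h (21.7 days). Both exceed the assumed range.

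**The case against.** The strongest reply is that Rac may never be reported, and that little depends on it. The SAP's own list begins "For the multiple dosing phase, Cmax, Tmax, Cmin, Cavg", continues with two AUCs and CL, and omits Rac. The sponsor performs and reports the PK analysis separately (SAP 3.6). Protocol 8.4.5 defers final PK methods to a PK analysis plan and/or the SAP; that plan is not available here, and 8.4.5 is partly redacted. No endpoint, test or dose decision is tied to Rac. All of this stands and limits the impact. It does not cure the rule: Rac is still defined in the SAP's table of parameter definitions and rules, and additional parameters may be reported. Summarising by dose does not help either, because a within-subject ratio across two doses belongs to no single dose stratum.

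Some stronger readings are tempting, but the documents do not support them:

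- *Priming cohorts would show Rac of 2.5 to 7.* That is 0.5/0.2 to 1.4/0.2, and it needs Week 1 as the reference. Both serial profiles are at the stable dose, so their dose ratio is 1. Only the wording mismatch and the sparse Week 1 sampling remain.
- *Rac is mostly dose change everywhere.* That holds for full ramps within the assumed half-lives. It can fail for a subject who stops at 0.3 mg/kg (39% at 156 h).
- *Combination Rac is 5.* Fivefold is a ceiling on the dose ratio. Some rituximab-combination treatment began at 0.2 mg/kg (Protocol 1.7), and intensification is required only for newly enrolled subjects. If the second profile is at the sixth infusion, a full ramp has just reached 0.5 mg/kg and is not at steady state.
- *Exposure–safety conclusions will be misled.* SAP 3.6.2 describes that work as optional, model-based and separately reported, and nothing says that it uses Rac.

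**Conclusion.** The point holds for Part 3 and for combination subjects who are intensified. As defined, Rac combines accumulation with a planned dose increase of up to 2.5-fold or 5-fold. A full Part 3 ramp gives about 2.6 to 4.7 where a constant dose gives 1.04 to 1.90. These figures rest on linear one-compartment kinetics and a half-life range borrowed from monkeys; the dose ratios themselves need neither assumption.

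A reader might infer that Part 1 and all unramped cohorts are safe by study part. They are not. Protocol 1.7 records that the 0.3 mg/kg subjects were to be reduced to 0.2 mg/kg (one went to 0.1), which would pull Rac down by a factor of 0.2/0.3 = 0.67 if it happened before the second profile. Protocol 3.2.1 allowed later escalation, and Protocol 1.8.3 reports 46 subjects intensified at investigator discretion. The unchanged-dose test therefore has to be made subject by subject.

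The consequence is confined to descriptive secondary PK reporting. It deserves correction because the stated rule gives a misleading number when followed and the repair is cheap.

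**What to change.** In SAP 3.6.2:

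1. Define Rac = (AUCtau,ss / dose at that profile) / (AUCtau,first / dose at the first profile).
2. Report the un-normalised ratio only for individual subjects whose actual dose was the same at both profiles, decided per subject and not by study part.
3. For priming cohorts, name Week 2 as the reference profile, to match Protocol 7.14.2.
4. Label the normalised ratio in dose-changing subjects as still mixing accumulation with any non-linear PK, since monkey Cmax and AUC "increased in a more-than-dose-proportional manner". Late ramps also leave carry-over from lower doses (1.59 in the table, against 1.90 at constant-dose steady state).
5. Reconcile the second serial profile for the combination cohorts, given as the sixth infusion in Protocol 7.14.2 and as Week 8 in Appendix D Table 1, and state which profile enters Rac.

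The cost is a short SAP edit, a table footnote and one clarification between two protocol passages. No new data are needed: administered doses are already collected for the exposure summaries and for clearance.
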